complete all assessments. In order to provide incentive to complete the follow-up assessments and to compensate participants for ongoing commitment to the research project, participants will receive additional compensation for the later assessments. Although rigorous attempts will be made to keep participants in the study and to gather complete data at each of the scheduled assessments, we conservatively anticipate up to 20% attrition and other incomplete data at the 12-week assessment due to factors outside our control (e.g. participant unwillingness, time constraints). In addition to planning for dropouts a priori by recruiting a larger sample, we plan to conduct intent-to-treat analyses (see below) to protect against potential bias that may occur when individuals drop out of the study due to their level of disability and their response to treatment and by using imputation methods for missing data as described below.

Data and Power Analysis for Sub-Study II

With 80 participants in the telehealth study (40 in each condition), assuming that 15% would not complete the post-treatment assessment, we would have sufficient (.80) power to show a medium-large between group effect (0.69). Importantly, we would also have .80 power to detect a medium (0.5) within-group effect.

Data Analyses for Specific Aims

The goal of the primary analysis is to determine whether participants in the Tai Chi Condition show more advantageous change in Brief Pain Inventory scores from baseline to 12-week assessment than those in the Wellness Condition. The analysis will follow an intent-to-treat approach (all randomized patients will be included in the analysis). The primary analysis will compare groups on the change from baseline Brief Pain Inventory to 12-week using generalized estimating equation (GEE) analysis of covariance adjusting for baseline score. The GEE analysis model will incorporate change from baseline to all patient visits through 12-week into the analysis, and will include main effects of treatment, visit, and the baseline score, and a treatment-by-time interaction effect. From this model, an assessment of the treatment difference on mean change from baseline to 12 weeks will be carried out on the robust estimates using a two-sided 0.05 level of significance. An unstructured correlation structure will be assumed as the within-patient correlation between time points.

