The primary analysis will be based on all available data. However, as supportive analyses, missing Brief Pain Inventory scores will be imputed at each visit in a monotone manner via multiple imputation linear regression approach and the above analysis will be repeated on the imputed data. Specifically, the imputation model will include important covariates such as age, gender, and baseline Brief Pain Inventory score. A total of 10 imputed datasets will be generated, and the above GEE analysis will be carried out on each imputed dataset; the Week 12 score results will be combined across the 10 datasets using the standard techniques for multiply imputed data sets in order to yield on overall Week 12 on the imputed data.

Similar analyses will be used for secondary endpoints. We anticipate that the distribution of the pain scale and scores on secondary outcome measures will be skewed, and that log transformed scores will be used in the analysis.

Human Subjects Research

a. Human Subjects Involvement and Characteristics

The participant population is to be comprised of up to 140 male and female Gulf War Veterans. These individuals will be recruited on a volunteer basis. Only individuals who provide written informed consent may participate. A participant may withdraw his/her consent at any time and without prejudice. A clear and detailed explanation will precede all procedures.

Informed consent will be obtained by the study PI or by another IRB-approved study staff member prior to the initiation of any study procedures. Informed consent will be reviewed with the participant at the beginning of this scheduled appointment, prior to initiating the assessment.

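### Does imputing Brief Pain Inventory scores by linear regression and then taking logs break the supportive analysis?

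*Combined protocol and SAP*

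**What the plan says.** In *Data Analyses for Specific Aims*, the primary analysis compares the arms on change in BPI from baseline to 12 weeks. It uses a GEE model on all available data, and no transformation is mentioned there. Imputation belongs to a supportive analysis: "missing Brief Pain Inventory scores will be imputed at each visit in a monotone manner via multiple imputation linear regression approach". On covariates, "the imputation model will include important covariates such as age, gender, and baseline Brief Pain Inventory score". Ten datasets are made, and "the above GEE analysis will be carried out on each imputed dataset".

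A separate closing paragraph first says "Similar analyses will be used for secondary endpoints" and then turns to transformation: "We anticipate that the distribution of the pain scale and scores on secondary outcome measures will be skewed, and that log transformed scores" are what the authors expect to analyse.

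The section does not say whether the log comes before or after imputation, what offset would handle a score of zero, or whether imputed values are bounded. The protocol describes the BPI items but gives no range, mean or SD for the score.

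*Participant Attrition and Missing Data* presents imputation as one protection against bias when "individuals drop out of the study due to their level of disability and their response to treatment". It also states that "we conservatively anticipate up to 20% attrition and other incomplete data at the 12-week assessment". The power statement for Sub-Study II assumes 15%.

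**The concern.** Read in the order in which the sentences appear, the plan imputes a score and then logs it. The object of imputation is a BPI score, and the log is attached to the later step: "log transformed scores will be used in the analysis". Regression imputation adds normal noise, so some imputed values can be zero or negative. That does no harm to a mean on the raw scale, but such a value has no logarithm, so the record drops out or has to be altered by hand.

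The lost records would be the lowest imputed pain scores, and so would come more often from the arm that is doing better. The right skew that would justify a log also makes these values more common and fits poorly with a normal imputation model. If all this held, the analysis meant to guard against outcome-related dropout would discard the records it was meant to supply. It could then look discordant with the primary result for no clinical reason. The sentence on similar analyses would carry the problem to the secondary endpoints.

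**Working it through.** **The plan's own figure.** With 40 per arm and 15% not completing, n = 40 × (1 − 0.15) = 34 per arm. A two-sample t-test at two-sided 0.05 with d = 0.69 has power 0.800, which matches the stated 0.80. Nothing below changes it.

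**Number of imputed week-12 values.** At 15% missing, 0.15 × 80 = 12 people, and 12 × 10 datasets = 120 values. At 20%, 16 people give 160 values.

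**Share without a log, if raw scores are imputed first.** For a normal draw, P(value ≤ 0) = Φ(−mean/SD). For log-normal scores with log SD s, mean/SD = 1/CV, where CV = √(exp(s²) − 1). The means, SDs and s are assumptions, because the documents give none.

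| Assumed scores | Mean/SD | Share ≤ 0 | Expected in 120 |
|---|---|---|---|
| Normal, mean 6, SD 2.2 | 2.73 | 0.3% | 0.4 |
| Normal, mean 5, SD 2.2 | 2.27 | 1.2% | 1.4 |
| Normal, mean 4, SD 2.2 | 1.82 | 3.5% | 4.2 |
| Log-normal, s = 0.5 (CV 0.533) | 1.88 | 3.0% | 3.6 |
| Log-normal, s = 0.6 (CV 0.658) | 1.52 | 6.4% | 7.7 |
| Log-normal, s = 0.8 (CV 0.947) | 1.06 | 14.5% | 17.5 |

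A fuller simulation used weekly visits, a treatment effect of 0.69 log SD and 15% missing. Its log-normal shares were 6.0%, 10.1% and 17.7%.

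**Effect on the result, missing at random, impute-then-log.** In that weekly GEE simulation (400 trials per case, Monte Carlo SE of power about 0.02), power for raw-score against log-scale imputation was:
- s = 0.5: 0.785 v 0.855
- s = 0.6: 0.772 v 0.805
- s = 0.8: 0.818 v 0.858
- s = 0.6 with 20% missing: 0.728 v 0.800

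The loss is therefore 3 to 7 points. Type I error under raw-score imputation was 0.020–0.035, so it was not inflated. In a simpler baseline-and-week-12 simulation, the mean contrasts against the true values (0.69 × s) were −0.348 v −0.345, −0.417 v −0.414 and −0.534 v −0.552. Those are differences of about 1%, 1% and 3%.

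**The other order.** If outcome and baseline are logged first (with an offset if zeros occur), imputation works on the log scale, where negative values are legitimate. The number of undefined values is then zero by construction, and the imputed logs go straight into the GEE.

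**Observed zeros.** On an assumed 0–10 score with 15% missing, at least one imputed value ≤ 0 and at least one observed score of 0 occur in similar shares of trials:

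| Week-12 mean, SD | Any imputed ≤ 0 | Any observed 0 |
|---|---|---|
| 6, 1.5 | 1.5% | 0.8% |
| 6, 2 | 21% | 21% |
| 4.5, 2 | 75% | 68% |
| 4, 2 | 88% | 87% |

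An analyst who logs the BPI would thus usually meet the zero problem in the observed data, before any imputation is run.

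**The case for a change.** The strongest case for a change is that impute-then-log is the natural reading, that the skew which motivates the log makes failure frequent, and that an unwritten repair is a choice made after data access. An offset alone does not remove the problem. With log(score + 1) and an assumed median of 3, raw-score imputation still leaves 2.0%, 4.6% and 11.6% of values undefined for s = 0.5, 0.6 and 0.8. If Tai Chi responders leave early, the simulated log contrast shrinks from −0.409 with complete data to −0.379 (0.030/0.409, about 7%), and power is 0.66 against 0.80 with log-scale imputation.

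The mechanism stands, and so does the observation that order and offset are not written down. The larger figures carry little weight, for three reasons.
- The responder case needs a weekly dropout hazard ten times higher for low scorers in one arm only (0.07 v 0.007), with 11 of about 15 missing people in Tai Chi. Nothing in the documents supports those values.
- The log-normal shape is a choice. With an assumed 0–10 scale and median 5, a share Φ(−ln 2/s) = 8–19% of such scores would exceed the maximum. Eligibility also requires at least six months of musculoskeletal pain or stiffness, which argues against scores crowded near zero.
- The power loss does not follow the count of undefined logs. The standard error rises 12% at s = 0.5 (0.130 v 0.116) with 6.0% undefined, but only 2% at s = 0.8 (0.190 v 0.187) with 17.7% undefined. Lost records are therefore not shown to be the main cause.

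**Conclusion.** The concern does not call for a change. The plan leaves the order of transformation and imputation open, and one of the two orders works without difficulty. The log sentence is an expectation that depends on the observed distribution, not a fixed instruction. The failure would also be visible: each imputed dataset should hold 80 week-12 scores, and one that falls short after logging prompts the analyst to transform first.

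Under the unfavourable order, about 0.3–3.5% (symmetric) to 3–18% (log-normal) of imputed values would be undefined. The cost would be some supportive power and very little bias if data are missing at random. All of these figures rest on BPI distributions that the documents do not give. The imputation route leaves the available-data primary analysis and the stated 0.80 power as they are, and the simulations show no inflation of type I error.

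Whether the BPI contrast itself is better on the raw or the log scale is a fair trade-off. In simulation, power on raw v log was 0.81–0.84 v 0.88–0.89 for log-normal scores, but 0.875 v 0.852 for symmetric ones.

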All discussions concerning consent will emphasize that participation is voluntary and that the Participant's medical care/benefits will be unaffected by his or her decision regarding participation. Participants will be informed that they will be compensated for time and travel at a rate of \$50 for the baseline and 12-week assessments, \$75 for the 24-week (approximately 3 month post Tai Chi) assessment and \$100 for the 48-week (approximately 9 month post Tai Chi) assessment for a total of up to \$275 for 4 assessment visits. Participants will also receive \$10 for use of video devices and inconvenience for each Tai Chi or Wellness session they attend, for a total of up to \$240. This remuneration for time, inconvenience, ongoing commitment, and travel is not so high as to coerce an individual to participate who would otherwise not participate.

b. Potential Risks

While the risks of the Tai Chi and Wellness protocols are minimal, there is some potential for injury from the exercises, including muscle tears, strain, sprains, and joint pain. In addition, participants may feel some stress, frustration, or boredom while completing the questionnaires. There will be a mental health professional available throughout the study for participants to talk with if needed.

The social risks of participating in this protocol are minimal. There may be some embarrassment as participants learn to do Tai Chi in a group with other participants, but the instructors will be trained to be very sensitive to the individual needs of each participant and create an environment that feels safe and nonjudgmental. There is no economic risk associated with participating in this study.

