All research material will be obtained specifically for research purposes. The sources of research material obtained from individually identifiable living human subjects in the form of records or data will be obtained specifically for this research project. All information pertaining to this project (e.g., screening forms, questionnaire data, interviews, audio recordings) will be held in the strictest confidence, will be kept in locked files or in password protected digital files on encrypted PCs with secure server and will be available only to individuals directly involved with the project. Under no circumstances will individually identifiable data be released to anyone without written consent of the participant. Results will be published as group findings only. Assessment and treatment results will be discussed with the participant only.

Data will be stored at this secure location:

\\r04bhsnas61\resgroups\$\PTSD\DATA\RESEARCH\TeleHealth - [name]\Tai Chi Studies\Gulf War Study\Data

d. Protection Against Risk

The following steps will be taken to minimize risk to participants who participate in the Tai Chi activity:

- Exclusion of individuals with comorbidities and any serious medical conditions that carry a potential risk.
- Warm-up and stretching exercises at the beginning of each Tai Chi session will be an integral part of the training program, because these maneuvers are known to prevent injury.

- The research team and Tai Chi instructors will provide participants with opportunities to report any potential negative effects they may be experiencing during the 12 weeks of Tai Chi. The research team and Tai Chi instructors will specifically ask patients if they have experienced any adverse events that may be associated with exercise (i.e. falling down, joint swelling, muscle aches) as part of this study.
- A research staff member (PI, Study Coordinator, or Research Assistant) will be present at all Tai Chi intervention classes. Research staff will be CPR certified before the initiation of the interventions. Research staff will be instructed to obtain immediate emergency care for any participants in case of an emergency.

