Participants will be informed that if suicidal or homicidal intentions are disclosed, confidentiality may be broken in order for protective measures to be taken. Although there will be no questions asked in the assessments regarding care of children or geriatric persons, if a participant were to disclose child or elder abuse, appropriate agencies would be contacted, and participants will be so informed in the consent form.

All personnel involved in this proposed project will have the required ethics, human subjects, and confidentiality training, which include information about maintaining data integrity and security. Careful monitoring of participants during all phases of study participation will be conducted by the project staff. Each participant will see the same clinicians for each of their treatment visits. Participants will be instructed to contact study personnel at any time (including during the follow-up interval) in the event of worsening of symptoms. Participants who begin treatment and experience adverse outcomes sufficient to require removal from the study will receive appropriate clinical care.

As in any type of treatment or clinical research program, participants' confidentiality must be carefully guarded and respected. All data with identifying information will be stored in locked files or password-protected computer files. Data being analyzed will be identified by subject codes, and identifying information will be removed. The identity of participants will not be revealed in the presentation or publication of any results from the project. All project staff working on the project will be educated about the importance of strictly respecting participants' rights to confidentiality and will have completed several training courses including proper practice in accordance with HIPAA regulations, protection of human subjects, and computer security.

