In the proposed study we will use the FDA definition of adverse events (AE) and serious adverse events (SAE). Any SAE, whether or not related to study intervention, will be reported within the required 10 day reporting period to the IRB and will be followed by an additional letter detailing the nature of the SAE. In the event that a participant either withdraws from the study or the PIs decide to discontinue a participant due to a SAE, the participant will be monitored by the investigators until (a) a resolution is reached (e.g., the problem has resolved or stabilized with no further change expected), (b) the SAE is determined to be clearly unrelated to the study intervention, or (c) the SAE results in death. Outcomes of SAEs will be regularly reported to the IRB. A summary of all AEs and SAEs that occurred during the previous year will be included in the annual IRB renewal. The study will be conducted at VA Boston Healthcare System. Under the arrangement to conduct the study on site at the VA facilities, the VA agrees to provide emergency services to anyone who participates in this project. We will specifically outline in the Informed Consent Forms the availability of emergency services to participants who may seek them during and after normal working hours. In the Informed Consent Form, we will provide specific information about emergency contacts. Participants are instructed to contact [name] or [name] during working hours. We will also provide a list of crisis hotline numbers and community resources that participants may access as well as making sure the Veterans have access to the Crisis Hotline for Veterans ([name]).

References

- Andersson, E. I., Lin, C. C., Smeets, Rob J E M, Linköpings universitet, & Hälsouniversitetet. (2010). Performance tests in people with chronic low back pain: Responsiveness and minimal clinically important change. *Spine*, 35(26), E1559-E1563. doi:10.1097/BRS.0b013e3181cea12e
- Anderson, K. O., Dowds, B. N., Pelletz, R. E., Thomas Edwards, W., & Peeters-Asdourian, C. (1995). Development and initial validation of a scale to measure self-efficacy beliefs in patients with chronic pain. *Pain*, 63(1), 77-83. doi:10.1016/0304-3959(95)00021-J
- Armitage, S. G. (1946). An analysis of certain psychological tests used for the evaluation of brain injury. *Psychological Monographs*, 60(1), i-48. doi:10.1037/h0093567

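### Active questioning about adverse events is described for Tai Chi only, so any by-arm description of non-serious events would be confounded by how they were collected

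*Combined protocol and SAP*

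**What the plan says.** The only active AE question in the protocol is under Protection Against Risk. The list it belongs to opens with "The following steps will be taken to minimize risk to participants who participate in the Tai Chi activity". Within that list, participants are to be given "opportunities to report any potential negative effects they may be experiencing during the 12 weeks of Tai Chi", and staff will "specifically ask patients if they have experienced any adverse events that may be associated with exercise", with falls, swollen joints and aching muscles named. The next item says that a member of the research staff "will be present at all Tai Chi intervention classes".

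For both arms, the same section states that "Careful monitoring of participants during all phases of study participation will be conducted by the project staff" and that "Participants will be instructed to contact study personnel at any time (including during the follow-up interval) in the event of worsening of symptoms". The Data Safety Monitoring Plan covers both arms once staff know of an event: all AEs go to a PI and then to the IRB, any serious AE is reported to the IRB within 10 days whatever its relation to the intervention, and "A summary of all AEs and SAEs that occurred during the previous year will be included in the annual IRB renewal".

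Following Randomization describes weekly telephone collection of measures, without limiting it to one arm. The content given is the weekly measures and feedback on the groups. The schedule table under Measures and Questionnaires has no AE row. Safety appears in the long-term goal at the start of Specific Aims, but not in Specific Aim 1 or 2. Data Analyses for Specific Aims contains no AE analysis.

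**The concern.** When one arm is asked about events and the other is left to volunteer them, the arm that is asked will usually record more, even at equal true risk. This population is exposed to that problem because every participant must enter with musculoskeletal or joint pain or stiffness of at least 6 months. Muscle aches, one of the prompted events, overlap the entry condition, so a count in Tai Chi is hard to interpret without the same question in Wellness to show the background. Delivery is by video, with daily home practice in the Tai Chi arm, so staff will not see most events and capture depends on asking.

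At stake is any statement that compares the two programmes on minor harms. The primary pain analysis is not affected.

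**Working it through.** **Step 1: routes by which staff learn of an event, by arm.**

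| Route | Tai Chi | Wellness |
|---|---|---|
| Direct question on exercise-type events | Yes, in the Tai Chi list | None described |
| Stated invitation to report negative effects over 12 weeks | Yes | None described |
| Participant-initiated contact on worsening | Yes | Yes |
| General monitoring (no question or interval given) | Yes | Yes |
| Weekly call (no AE question described) | Yes | Yes |
| Health Symptom Checklist (HSC) at pre, post, 3 and 9 months; weekly Brief Pain Inventory (BPI) | Yes | Yes |
| Onward reporting of AEs and serious AEs once known | Yes | Yes |

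The arms differ in the first two rows only. The last row governs what happens after staff learn of an event, so it does not equalise detection.

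**Step 2: whether the questionnaires fill the gap.** The HSC has a 30-day recall. Treatment lasts 12 × 7 = 84 days, so the post-treatment checklist reaches back over about 30/84 = 36% of it. The BPI records pain weekly. Neither is described as an AE form or as recording falls.

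**Step 3: size, on assumed inputs.** The plan states no AE rate, capture rate or safety sample size, so there is no figure of its own to reproduce. The only input taken from the plan is 40 per arm (Data and Power Analysis for Sub-Study II). Assumed: equal true risk p in both arms, from 10% to 40%; capture 90% when asked; capture c from 30% to 90% when not asked.

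Observed risk = true risk × capture. With equal true risk, p cancels and the observed risk ratio is 0.90/c:
- c = 90%: 0.90/0.90 = 1.0
- c = 60%: 0.90/0.60 = 1.5
- c = 30%: 0.90/0.30 = 3.0

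Expected participants with a recorded event at p = 30%:
- Tai Chi: 40 × 0.30 × 0.90 = 10.8
- Wellness, c = 60%: 40 × 0.30 × 0.60 = 7.2
- Wellness, c = 30%: 40 × 0.30 × 0.30 = 3.6

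To show how persuasive such a table could look, the chance that a two-sided Fisher test gives p < 0.05 with no true difference was found by summing exact binomial probabilities over all possible pairs of counts at 40 per arm. The plan does not propose this test.

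| Unprompted capture | Chance at p = 30% | Range for p = 10% to 40% |
|---|---|---|
| 90% | 2.9% | 1.4% to 2.9% |
| 60% | 10.9% | 2.1% to 15.2% |
| 30% | 47.1% | 5.4% to 64.9% |

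**The case against.** The strongest reply is that no planned comparison is harmed. The Specific Aims concern pain, fatigue, cognition, quality of life and physical functioning; the analysis plan has no safety endpoint; and the yearly IRB summary is not said to be by arm. This stands, and it limits the point to any by-arm description of AEs that is made later.

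Wellness is also not left to chance. It meets twice a week under group leaders who are study staff or are research-credentialed and added to the study. Participants are telephoned weekly, and both arms have interviews at post-treatment and follow-up. This stands as well: unprompted capture in Wellness may be fairly high, and at 90% the assumed bias disappears. None of these contacts, however, is described as including an AE question.

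The section exists to protect participants, and asking about exercise harms where exercise is taught suits that purpose. Potential Risks begins "While the risks of the Tai Chi and Wellness protocols are minimal, there is some potential for injury", but the sentence goes on to tie the named injuries to the exercises, so it is not evidence that Wellness carries the same injury risk. The reason to ask in Wellness is to learn the background rate.

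Finally, the quoted question refers to patients in the study generally and names the research team, so it may have been meant for both arms. The list's opening line points to Tai Chi, and nothing elsewhere extends it. If both arms were intended, the text needs to say so.

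**Conclusion.** As written, active questioning about exercise-type events is described for Tai Chi only. Non-serious events would tend to be captured more fully there, and any by-arm description of AEs would be confounded by the method of collection, with the likely bias against Tai Chi. The illustrative risk ratio of 1.0 to 3.0 rests wholly on assumed capture rates; the documents cannot place the trial within that range or exclude values outside it.

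A reader might infer more than the documents support:
- **That a trial objective fails.** Safety is a long-term programme goal, not a Specific Aim, and no between-arm AE test is planned.
- **That serious events would be missed in Wellness.** The rule for reporting serious AEs and the instruction to contact staff are the same in both arms.
- **That background musculoskeletal complaints would be unknown.** The HSC and weekly BPI give some information in both arms, though not as AE records.
- **That Tai Chi's harms could not be described at all.** Its events are the ones being sought, so its own experience can be reported. What is weakened is the comparison with Wellness.

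**What to change.** Ask one fixed AE question (falls, joint swelling, muscle aches, other) on the existing weekly call in both arms, with the same wording and recall period, for the 12 weeks. Add an AE row to the assessment schedule, and state that AEs will be tabulated by arm. The existing Tai Chi class procedures can stay as a protective measure, but the tabulation should identify events found by the common weekly question, so that like is compared with like.

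The cost is one or two extra questions per call and more recorded minor events in Wellness, which will need to be processed and reported. No new visits are needed, and the sample size does not change. For participants whose 12 weeks are already over, the question cannot be asked retrospectively on the same footing; any by-arm table that includes them should state how their events were collected.
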